COLLABORATING TO HEAL ADDICTION AND MENTAL HEALTH IN PRIMARY CARE (CHAMP)

STATISTICAL ANALYSIS PLAN (SAP) **1/24/2023**

Multiple Principal Investigators - [name]; [name]; [name]

Authors - [name], [name], [name]

Version - 5.0 (8/30/2024)

Grant Number: UF1MH121942

National Clinical Trial (NCT) Identified Number: NCT04600414

Sponsor: National Institute of Mental Health (NIMH)

Modifications to the CHAMP Statistical Analysis Plan

Change	Reason	Date
In shell Table S2 changed " Change to 3 months " to " 3 months " and " Change to 6 months (primary outcome) " to " 6 months (primary outcome) "	To simplify the calculation of the SE for the adjusted mean differences in order to calculate the confidence interval	5/6/24
Replacing adjusted mean difference with AOR for opioid use primary outcome	Calculating SE for adjusted means from logistic model requires use of the delta method, so	6/18/24

Reporting Cohen's d without confidence intervals	confidence intervals are less interpretable (i.e., contain 0 for significant effects)	
	We will report confidence intervals for the AOR. (see above regarding calculating SE for logistic model).	6/18/24
Test moderated mediation by analyzing moderation first	Because we planned to conduct these analyses separately (mediation, then moderation), the presence of a moderation of $M \rightarrow Y$ violates an assumption of mediation.	8/8/24
Added mean, standard deviation, and 95% confidence intervals to secondary outcomes table (Table S3). Omitted recent overdose covariate from main models.	To provide additional detail to assist with interpretation of secondary outcome results. To help with model convergence.	8/30/24

Table of Contents

1. Introduction	4
2. Study design	4
3. Outcomes	4
4. Analyses	6
4.1. Primary and Secondary Outcomes (Hypotheses 1 and 2).....	6
4.2 Moderated Mediation Analyses (Hypothesis 2)	8
5. Missing data	9
6. Power Calculation	10
7. References.....	11
8. Shell Tables and Figures	13
Table S1. Baseline characteristics of patients enrolled in SPIRIT	13
Table S2. Multiple primary outcomes across intervention conditions.....	17
Table S3. Treatment effects for secondary and exploratory outcomes at 3 and 6 month follow-up....	18
Table S4a. Moderation analysis.....	20
Table S4b. Mediation analysis	20

1. Introduction

In 2018, the National Institute of Mental Health (NIMH) issued a Request For Applications (RFA-MH-19-525) titled “Helping to End Addiction Long-term (HEAL) Initiative: Effectiveness Trials to Optimize, Implement, Scale, and Sustain the Collaborative Care Model for Individuals with Opioid Use Disorders and Mental Health Conditions”. Four clinical trials were funded, including the Collaborating to Heal Addiction and Mental Health in Primary care (CHAMP) trial described in this manuscript. The objective of the CHAMP trial was to compare the effectiveness of a Collaborative Care Model (CoCM) intervention designed to co-manage both Opioid Use Disorder (OUD) and common co-occurring Mental Health Symptoms (MHS) to a usual care control condition representing CoCM designed to manage co-occurring MHS only.

This statistical analysis plan (SAP) will comprehensively enumerate the primary and secondary outcomes, and mediating variables, and corresponding analyses.

2. Study design

The CHAMP hybrid type 2a effectiveness-implementation trial was a cluster randomized trial in which clinics were randomized to CoCM for OUD and MHS or CoCM for MHS only. Hybrid type 2a trials compare two clinical interventions and pilot test a practical, but not evidence-based, implementation strategy.

Randomization - Initially 24 clinics were stratified according to one of two CoCM fidelity cohorts (specified as low or high) and healthcare organization and then randomized in a 1:1 ratio by our statistician into one of two arms (intervention or control). Stratification served two purposes. First, stratifying on healthcare organization (each has 2 or 4 clinics in the study) should balance the intervention and control groups according to key system level factors that influence quality and outcomes (e.g., electronic health record quality). Second, stratifying on cohort ensures balance with regard to fidelity to the CoCM model which is likely to be correlated with our primary outcomes. In addition, clinics with lower fidelity were designated to have a longer training duration. An additional 18 clinics were recruited later during the study and they all received the short training duration in order to maximize recruitment, and therefore we did not stratify the randomization of the additional 18 clinics by fidelity but did continue to stratify by health care system.

3. Outcomes

Primary outcome. There are two primary outcomes (see Table 1). Opioid use is one of our primary outcomes and is measured using item 7E from the Brief Addiction Monitor-Revised (BAM-R) which was derived from the Addiction Severity Index35 by CESATE: “7. In the past 30 days, how many days did you use any of the following drugs: E. Opiates (e.g., Heroin, Morphine, Dilaudid, Demerol, Oxycontin, oxy, codeine (Tylenol 2,3,4), Percocet, Vicodin, fentanyl, etc.)?” Our other primary outcome is mental health related quality of life and is being measured using

the Veterans Short Form Health Survey 12 Mental Health Component Summary score (MCS). Both primary outcomes are assessed at the 6-month follow-up survey.

Secondary outcomes. This study includes 24 secondary outcomes, assessed at both the 3-month follow-up and the 6-month follow-up (Table 1). Secondary outcomes include the use of other drugs, depression, anxiety, PTSD, pain, physical health-related quality of life and perceived access to OUD care (see Table 1). Secondary outcomes also include opioid use and mental health related quality of life assessed at the 3-month follow-up survey. Exploratory outcomes are risk factors for premature mortality, including suicidal ideation, discontinuing MOUD, overdose, suicide attempts, emergency department admission, and hospitalization. Risk factors are collected via survey and adverse event reporting.

Construct/Instrument	Instrument(s)	Baseline	3-Month Follow-Up	6-Month Follow-Up
Multiple Primary Outcomes				
Opioid Use	BAM-R ^{1,2}	X	X	X
Mental health related quality of life (MCS)	Veterans Short Form-12 ³	X	X	X
Secondary Outcomes				
Pain	PEG ⁴	X	X	X
Alcohol Use	AUDIT-C ⁵	X	X	X
Cannabis Use	BAM-R ^{1,2}	X	X	X
Other Drug Use	BAM-R ^{1,2}	X	X	X
Depression	SCL-20 ⁶	X	X	X
Anxiety	PROMIS Measure - Anxiety, Short Form ^{7,8}	X	X	X
PTSD	PCL-5 ^{9,10}	X	X	X
Physical health related quality of life (PCS)	Veterans Short Form-12 ³	X	X	X
Access to Care	APAC ¹¹	X	X	X
Exploratory Outcomes				
Risk factors for mortality	WFS ¹ and Adverse Events	X	X	X
Mediator Variable				
MOUD Consistency	WFS ¹	X	X	X

APAC - Assessment of Perceived Access to Care

BAM-R - Brief Addiction Monitor-Revised

ICR - Individual Change Readiness

MOUD – Medications for Opioid Use Disorder

PCL-5 - PTSD Check List

PC-PTSD-5 – Primary Care PTSD Screen for DSM-5

PCS - Physical health related quality of life

PEG - Pain, Enjoyment of Life and General Activity

PTSD – Posttraumatic Stress Disorder

SCL-20 - Hopkins Symptom Checklist

WFS – Written For Study

Mediator variables

The hypothesized mechanism of action is engagement in MOUD, which we define as initiation and “consistent” refilling of the MOUD medication, which has been demonstrated to be correlated with good outcomes.¹² MOUD consistency is defined as the ratio of the number of days they reported taking the MOUD medication (numerator) to the number of days during the reporting period for which it was prescribed (denominator).¹² This is measured from self-reported MOUD use in the past 30 days which is assessed using survey questions written for the study.

4. Analyses

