less illicit opioid use.⁴³ Of the three antidepressant trials with patients in methadone treatment, two demonstrated positive benefits of tricyclics (for depression symptoms but not OUD outcomes)^{44,45} and one found no benefit of an SSRI.⁴⁶ Importantly, the one previous CoCM trial focused on patients with OUDs and alcohol use disorders (SUMMIT trial) found that the proportion of patients remaining abstinent from opioids in the past 30 days was no higher in the CoCM group than the usual care group ($p=.33$).⁴⁷ However, only 13.4% of the patients in the CoCM group received MOUD compared to 12.6% in usual care ($p=.053$)⁴⁷ suggesting that difficulties with *implementation* were driving results rather than the ineffectiveness of MOUD in the context of CoCM. This highlights the critical importance of using effective implementation strategies to support the delivery of MOUD for OUD in the context of CoCM for MHS.

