Intent to Treat Analysis of Secondary Outcomes and Clinical Mechanism of Action of Effectiveness Trial - Measurement occasions (level 1) will be nested within individuals (level 2) and nested within clinics (level 3). All outcomes will be analyzed with a multilevel model accounting for clustering of observations (level 1) within patients (level 2) and clinics (level 3). Regression models will be specified with the appropriate distribution and link functions to match the dependent variable (linear for the continuous scores, logistic for MOUD engagement and presence of risk factors). The model includes a random intercept and random linear slope to account for person-level clustering and estimate variable time trends across participants. To allow for curvilinear change over time, time will be entered as a nominal variable by including dummy codes for the 3- and 6-month time points. The explanatory variable of interest will be group randomization status (e.g., intervention versus control). Main effects and interaction terms capture the difference between intervention and control group at each wave. Covariates will be included if they are theoretically related to both the dependent variable and the probability of having missing data. An alpha level of 0.05 and two-tailed tests will be used to determine statistical significance. Results for continuous variables will be presented as adjusted differences between groups with confidence intervals. Results for dichotomous variables will be presented as

adjusted odds ratios with confidence intervals. **Missing Data** - We will examine patterns of missing data to determine the degree to which the missing at random assumption (the degree to which missingness is related to variables included in the model) is plausible. With high missing rates, we may use missing data methods to account for missing not at random mechanisms. If warranted, multiple imputation or similar methods will be used to account for missing data on completed or partially completed baseline and follow-up surveys (e.g., skipped items).

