4.2 Moderated Mediation Analyses (Hypothesis 2)

Hypothesis 2: MOUD consistency will fully mediate any improvements in patient-reported outcomes observed in intervention clinics compared to control clinics.

These analyses will compare the different pathways through which the intervention transmits effects. We hypothesize that the intervention should lead to greater use of MOUD (A path in Figure 2) because of the care managers' encouragement of MOUD initiation and adherence, leading to improved outcomes. We also expect the intervention will cause MOUD use to be more effective (Moderation path in Figure 3) in improving outcomes because of the use of the OTRI measurement-based care instrument and dosage recommendations by the consulting psychiatrist. Because the proposed moderation violates the assumption of mediation, we will first test the moderation (Figure 3), followed by a mediation or moderated mediation analysis (Figure 2).^{13,14} This analysis will be performed in three stages. In the first stage, we will use the same model as described in equation 1 to assess the MOUD consistency x intervention (moderator) interaction (Figure 3) (Table S4a). In the second stage, we will test the effect of the intervention on the mediator (A path in Figure 2) (Table S4b). In the third stage, the mediator will be included (B path), controlling for the direct effects of treatment (C path in Figure 2) (Table S4b). If the moderation is statistically significant, the MOUD consistency x intervention interaction will be included in this model. Models will be run separately for 3- and 6-months.

Figure 2. Path diagram for mediation model

[figure not shown]
[figure not shown]

Figure 3. Path diagram for moderation model

For the moderation analysis, we use the same model structure and design variables as the primary outcome. We will include MOUD consistency and intervention as main effects and the MOUD Consistency x intervention interaction. (Table S4a).

To calculate A path, the main effect of treatment on the mediator, we will use the same model as the primary outcome (Table S4b). Direct effects on MOUD consistency (path A) will be presented as an adjusted mean. To account for the potential imbalance of the mediator across the intervention and control groups at baseline due to the small number of clusters, the main effect for intervention at baseline is included.

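### The MOUD mediator (days taken / days prescribed) has no stated value for patients with no prescription, so whether path A can show initiation depends on an unwritten coding rule

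*SAP*

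**What the plan says.** **Construct.** SAP section 3 (Mediator variables) states: "The hypothesized mechanism of action is engagement in MOUD, which we define as initiation and" consistent refilling. Protocol 4.1, Hypothesis 2b, gives initiation and adherence as examples of engagement. SAP 4.2 says that "the intervention should lead to greater use of MOUD (A path in Figure 2"), because care managers encourage patients both to start and to adhere.

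**Variable.** The one mediator in SAP Table 1 and in shell Tables S4a and S4b is MOUD consistency: days the patient reports taking MOUD, over the "number of days during the reporting period for which it was prescribed (denominator"). On the window the SAP says: "This is measured from self-reported MOUD use in the past 30 days". Protocol 6.1.1, 6.4 and 9.4.3 give the same ratio over the 6-month follow-up.

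**Model.** SAP 4.2 says: "Direct effects on MOUD consistency (path A) will be presented as an adjusted mean". Protocol 9.4.3 instead plans models that are "linear for the continuous scores, logistic for MOUD engagement and presence of risk factors", without a cut-off for engagement. That paragraph is headed "Intent to Treat Analysis of Secondary Outcomes and Clinical Mechanism of Action of Effectiveness Trial".

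**Patients with no prescription.** Neither document states a value or an inclusion rule for them. SAP section 5 specifies maximum likelihood under missing at random, which concerns values that exist but were not observed.

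**The concern.** Patients with no prescribed days are foreseeable. Control clinics refer patients elsewhere for OUD treatment, although their providers may prescribe (Protocol 6.1.1). Treatment engagement is optional in both arms, and treatment may be stopped at any time (Protocol 6.1.1, 7.1). For such a patient the mediator is 0/0. Unless someone writes a rule, an analysis program will normally make that missing.

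Paths A and B and the moderation model would then describe adherence among people who were prescribed MOUD. Prescribing can begin after enrolment, and intervention providers are expected to prescribe, so that group is partly a product of the intervention.

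Hypothesis 2 claims full mediation, and SAP 4.2 tests the indirect effect as path A times path B. If the intervention works mainly by getting more patients onto MOUD, that route could be rejected because the variable cannot show it. Two analysts could follow the SAP as written, code these patients differently, and report different mediation results.

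**Working it through.** The plan states no expected value or power for the mediator, so there is no figure to reproduce. The check is what path A equals under each possible coding.

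**Inputs.** For arm I (intervention) or C (control):
- p = share prescribed MOUD in the 30-day window
- c = share of the 30 days covered by a prescription, among those prescribed
- a = days taken / days prescribed, among those prescribed

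The documents give none of these for this trial, so all values below are assumptions. The arms are taken as equal at baseline, so that the SAP's arm-by-time contrast equals the follow-up difference.

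**Formulas for path A**
- Ratio, unprescribed patients dropped: aI − aC
- Ratio, unprescribed patients coded 0: pI·aI − pC·aC
- Days taken / 30, all patients: pI·cI·aI − pC·cC·aC

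**Results** (c = 1 in both arms except in the last row)

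| Prescribed, I v C | Adherence, I v C | Dropped | Coded 0 | Days / 30 |
|---|---|---|---|---|
| 60% v 50% | 0.80 v 0.80 | 0.00 | +0.08 | +0.08 |
| 60% v 30% | 0.80 v 0.80 | 0.00 | +0.24 | +0.24 |
| 60% v 15% | 0.80 v 0.80 | 0.00 | +0.36 | +0.36 |
| 60% v 30% | 0.90 v 0.80 | +0.10 | +0.30 | +0.30 |
| 60% v 30% | 0.80 v 0.90 | −0.10 | +0.21 | +0.21 |
| 50% v 50%, covered 30 v 15 days | 0.80 v 0.80 | 0.00 | 0.00 | +0.20 |

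Second row in full: dropped, 0.80 − 0.80 = 0.00; coded 0, 0.60 × 0.80 − 0.30 × 0.80 = 0.48 − 0.24 = +0.24. The zeros in the dropped column follow directly from equal adherence. When path A is 0, the product A × B is 0 whatever path B is.

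In the fifth row the sign reverses: fewer control patients start, but those who do adhere better.

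**How many patients have no ratio.** If the 254 enrolled (SAP section 6) split evenly and all were surveyed, the count is 127 × (2 − pI − pC). At 60% v 50% this is 127 × 0.9 = 114 (45%). At 60% v 30% it is 127 × 1.1 = 140 (55%).

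**Coverage within the window.** 7/7, 15/15 and 30/30 all give a ratio of 1.00. Days taken / 30 gives 0.23, 0.50 and 1.00. Protocol 6.1.1 describes supplies of 7 to 30 days.

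**The case against.** Four points can be made for the plan.

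1. **The ratio is the mediator the plan names.** Protocol section 3 speaks of persistent use, Protocol 6.1.1 defines the mechanism as persistence and gives this ratio, and SAP Hypothesis 2 names MOUD consistency. This stands as a reason to keep the ratio as a reported analysis. It does not supply a value for unprescribed patients, nor does it reconcile the ratio with SAP 3 and 4.2, which bring in initiation.

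2. **The harmful coding is not established.** A reader might infer that the planned path A necessarily misses initiation. The documents do not support that. The intent-to-treat heading in Protocol 9.4.3, and the wording there and in 6.4 about whether the patient engaged, suggest an all-patient variable. The survey items were written for the study and are not shown, so what an unprescribed patient records cannot be checked. If such patients are coded 0, initiation is recovered.

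3. **Coverage is not lost altogether.** A reader might also infer that the ratio ignores length of coverage however it is coded. That goes too far. With zeros coded at each wave, a patient who has lapsed by 3 or 6 months scores 0 there. What is lost is variation within the 30 days among patients who were prescribed something.

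4. **The rates are speculative.** Some patients may already be on MOUD at enrolment (Table S1 has a row for current MOUD), and control providers may prescribe, so a large arm gap is not assured. It is tempting to borrow the MOUD rates of the earlier collaborative care trial in Protocol 2.2. That trial also covered alcohol use disorder, so its rates are a poor guide here and are not used.

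The conflict of window and model between the documents is minor. Protocol 9.4.1 provides for a formal SAP, and the SAP gives one window and one presentation of path A.

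**Conclusion.** The omission is certain. The sole mediator cannot be computed for a patient with no prescribed days, and no rule is given, although the SAP's own account of the mechanism includes initiation.

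The consequence is conditional. If these patients become missing, path A measures adherence in a subset formed after randomisation and cannot show an arm difference in starting treatment. Under the assumed 60% v 30% with equal adherence of 0.80, the choice of coding moves path A from 0.00 to +0.24. At 60% v 50% the shift is only 0.08. If they are coded 0, the remaining weakness is narrow: a short course within the window scores the same as full coverage.

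All prescribing and adherence rates are assumptions, and the result bears on Hypothesis 2 only. The tests of opioid use and mental health functioning are not affected. This should be fixed before the mediation results are interpreted.

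**What to change.** - **Mediator.** For the mediation and moderation models, use self-reported days taking MOUD in the past 30 days, divided by 30, for every patient surveyed at that wave, set to 0 if none. First confirm that the survey items give this for every patient.
- **Injections.** State one rule, the same in both arms, for counting days covered by extended-release injections. Registry records of injections (Protocol 6.1.2) may miss those given at referral sites, which matters more in control.
- **Consistency ratio.** Keep it, as named in Hypothesis 2, as a reported analysis among prescribed patients, with the number and percent prescribed by arm and wave.
- **Alignment.** Bring the Protocol 9.4.3 window and model into line with SAP 3 and 4.2. If a yes/no engagement variable is kept, state its cut-off.
- **Dating.** Date the change relative to unmasking. If it comes after, report both versions and label the new one post hoc.

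The cost is SAP wording, a check of the survey items and a recode. The downside is that days / 30 combines initiation with adherence, so the wording of Hypothesis 2 must be aligned and the two components shown beside it. The smallest step, stating a value for patients with no prescribed days, removes the undefined case but leaves the ratio insensitive to coverage within the window.

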4.1. Primary and Secondary Outcomes (Hypotheses 1 and 2)

Hypothesis 1: Compared to patients with MHS and OUD at clinics randomized to the control, patients at clinics randomized to the intervention group will report better access to and engagement in OUD treatment, less opioid use (primary outcome), better mental health functioning (primary outcome), fewer disorder specific mental health symptoms, better quality of life, and fewer risk factors for premature mortality (exploratory outcome).

All outcomes will be analyzed with a multilevel model accounting for clustering of observations (level 1) within patients (random effects at level 2) and clinics (random effects at level 3). The combined equation for the basic multilevel model applicable to a quantitative outcome such as mental health quality of life is as follows:

$$\begin{aligned} Y_{cit} = & \beta_0 + \beta_1(\text{Intervention}) + \beta_2(3 \text{ months}) + \beta_3(6 \text{ months}) \\ & + \beta_4(\text{Intervention} \times 3 \text{ months}) \\ & + \beta_5(\text{Intervention} \times 6 \text{ months}) + \beta_6 \text{DesignVars}_c \\ & + [u_c + u_{ci0}(\text{baseline}) + u_{ci3}(3 \text{ months}) + u_{ci6}(6 \text{ months})] \quad (\text{Eq. 1}) \end{aligned}$$

where c = clinic, i = patient, t = time

t_0 = baseline

t_3 = 3-month follow-up

$t_6 = 6$ -month follow-up

Here the outcome measured at time t , for subject i , in clinic c is denoted by Y_{cit} . To account for the cluster-randomization this model includes a random effect for each clinic denoted as u_c . In order to allow a general longitudinal correlation and variance structure we use three subject-specific error terms denoted by u_{cit} for $t=0, 3, 6$ months. We assume a general 3×3 covariance model for these error terms to provide maximal validity to inference regarding change over time. To allow for potential non-linear change over time, we will enter time as a nominal variable by including dummy codes for the 3 and 6 month time points represented by the variables (3 months) and (6 months). Intervention main effects and interaction between intervention and time indicators capture the difference between intervention clinics and control clinics at each wave – with β_1 representing the adjusted mean difference across intervention groups at baseline (adjusting for the design variables) -- with $\beta_1 + \beta_4$ representing the adjusted mean difference across intervention groups at 3 months – and with $\beta_1 + \beta_5$ representing the adjusted mean difference across intervention groups at 6 months. Therefore, the primary contrasts are given by with β_4 as the 3-month intervention effect, and β_5 as the 6-month intervention effect. Note that each intervention effect accounts for the potential imbalance of outcomes across the intervention and control groups at baseline due to the small number of clusters (β_1) and this is removed from the cross-sectional mean contrasts at each follow-up time to define the key intervention effect parameters. *DesignVars* denotes a vector of covariates that includes: 1) low vs high fidelity, which must be controlled because it was a design/stratification variable for some clinics, and 2) additional covariates theoretically related to both the primary outcome and the probability of not completing follow-up surveys which will aid in enhancing validity against missing data and improving precision of estimation. Specifically, we will include: 1) worried about not have stable housing in the next two months, 2) being on parole or probation and/or presently awaiting charges, trial or sentencing, 3) opioid craving, 4) pain, 5) Audit-C, 6) provider trust (APAC item #6), and 7) any use of other drugs (dummy coding for each class of drug). The pre-specified primary effect of interest will be β_5 , which represents the difference in change from baseline between intervention and control clinics at 6 months. Table S2 presents a shell table for the primary outcome and Figure 2 presents a shell plot. Table S3 presents a shell table for the secondary outcomes.

For the primary outcome (mental health related quality of life [0-100]) we will use a linear mixed model with a normal distribution with a linear link function and model structure given above in Equation 1. For the primary outcome days-using-opioids [0-30] we will modify the above linear mixed model and adopt a similar regression structure using a generalized linear mixed model with binomial distribution logit link function. We will retain the random effect structure to include a random effect for clinic and include the time-specific subject-level error terms to both allow for binomial overdispersion and a general longitudinal covariance over time. For the secondary and exploratory outcomes, appropriate link functions will be used for linear, binary (logit), ordinal (logit), and count (Poisson/negative binomial depending on dispersion) data. For any binary longitudinal outcomes, we will simplify the subject-level random effects to be a simple random intercept due to identifiability (no overdispersion and only correlation).

Effect sizes. Cohen's d effect sizes will be calculated and presented with 95% confidence intervals. Between group effect sizes will be calculated as the model-estimated treatment effect at each time point divided by the pooled, raw baseline standard deviation.

Testing of Multiple Primary Outcomes. The intervention will be interpreted to have been successful if there is a significance group difference between either primary outcome, not necessarily both primary outcomes. Corrections for multiple testing will be computed using a Bonferroni correction for the two multiple primary outcomes and therefore we will use an $\alpha=0.05/2 = 0.025$ to test each primary outcome. All secondary outcomes are exploratory and no multiple testing adjustment will be used. We will present secondary and exploratory outcomes descriptively using a forest plot to illustrate the collection of associations with intervention.

